### 7.2 Descriptive Statistics

For continuous variables, descriptive statistics will include the number of subjects (n), mean, standard deviation (SD), median, minimum and maximum. Categorical variables will be summarized using absolute and relative frequencies (i.e., counts and percentages). For categorical analyses, eyes that receive rescue therapy will be considered as treatment failures. Safety and PK data will be analyzed as collected.

All efficacy data will be summarized by treatment groups and overall using appropriate descriptive statistics. Summaries will be presented for both the MITT and PP populations, where applicable. Due to the small number of subjects enrolled at each center, all summaries and analyses will be performed using data pooled across centers. Unscheduled data, such as information from unscheduled visits or investigator comments, will be included in the data listings. In general, these data will be excluded from the summary tables unless otherwise specified.

### **7.3 Study Days Relative to First Day of Treatment**

Baseline results will be those recorded just prior to dosing. In cases where more than one pre-dose observation has been recorded, the last recording will be identified as the baseline result. Study days will be numbered relative to the first day of dosing. The start of study (Day 1) will be defined as the date on which a subject takes the first dose of any study medication, as recorded on the CRF. Relative to study start, days will be numbered ..., -2, -1, 1, 2, ... with Day 1 data collected on the first day of dosing prior to the start of study medication (Pre-Dose). Recorded data will be assigned to evaluation/assessment windows.

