Center will be used for final statistical analyses. Reading center personnel will be masked to subject treatment and the reading and grading will be done in a masked fashion.

Randomization will be stratified by study eye screening ETDRS DRSS (levels 43, 47 and 53 equally distributed between the treatment groups). The number of study eyes with moderate severity of DR (level 43) will be limited to 50.

Spot UACR and eGFR will be assessed as exploratory assessments to evaluate for any potential effects on renal function. UACR will be evaluated at Baseline, Month 6, Month 9, and Month 12 (EOT). eGFR will be evaluated at Screening, Baseline, Month 6, Month 9, and Month 12 (EOT).

Plasma samples will be collected at specified times on Day 1 and Month 6 visit for PK assessments. These samples will be analyzed for AKB-9778 using validated bioanalytical methods.

A blood sample will be retained for exploratory genetic analysis that may provide insight into the role of the VE-PTP/Tie2 pathway in diabetic retinopathy and an individual subject's response to AKB-9778 treatment. Similarly, blood samples collected at baseline and Month 12 End of Treatment (EOT) will be retained for exploratory analysis of biomarkers in plasma associated with VE-PTP inhibition and Tie2 activation. Once results of the study are known, the Sponsor will determine the value of conducting the genetic and biomarker assessments.

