9 STUDY PROCEDURES AND SCHEDULE OF ACTIVITIES

Please see [Appendix A](#) for a detailed table of the Schedule of Activities.

A one-month duration in this study is defined as 4 weeks/28 days. The 12-month Treatment period is 48-weeks/336 days.

This study includes the following periods and visits:

- Screening visit (up to 28 days prior to Baseline)
- Baseline visit (pre-dosing period on Day 1)
- Treatment Period (Days 1 through Month 12 (Week 48)); including:
 - Investigative site visits on Day 1, Day 7 (phone-call), and monthly (i.e., every 4 weeks) thereafter until the Month 12 (Week 48) EOT visit
 - Homecare nurse visits on Screening and Months 3, 6, 9, 12 (EOT)
- Follow-Up Period 1 Month (4 weeks) Post-Treatment

The following sections describe the procedures to be completed during the study. Subjects are to be assessed by the same Investigator or site personnel whenever possible.

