- Pregnancy test: A serum pregnancy test will be performed at Screening for females of childbearing potential. The investigative site will perform a urine pregnancy test at the Baseline, Month 6 and Month 12 EOT visits. The Screening and Baseline results must be available and must be negative before the subject takes the first dose of any study medication on Day 1. At each monthly visit, the site will query subjects of childbearing potential regarding the potential for pregnancy.
- Hematology: The complete blood count (CBC) will include: hemoglobin (Hgb), hematocrit, red blood cell (RBC) count, mean corpuscular (cell) volume (MCV), mean corpuscular hemoglobin (MCH), mean corpuscular hemoglobin concentration (MCHC), red cell distribution width (RDW), mean platelet volume (MPV), white blood cell (WBC) count with differential (neutrophils, immature granulocytes, lymphocytes, monocytes, eosinophils, basophils), platelet count, reticulocyte count and HbA1C. Hematology will be assessed every other month except for HbA1C which will be assessed at Screening, Baseline, Month 6, and Month 12 (EOT) visits.

Chemistry: The serum chemistry will include the following assays: sodium, potassium, bicarbonate, chloride, calcium, phosphorus, glucose, creatinine, blood urea nitrogen (BUN), creatinine phosphokinase (CPK), uric acid, albumin, total protein, total bilirubin, alkaline phosphatase, alanine transaminase ((ALT (SGPT)), aspartate transaminase (AST (SGOT)), lactate dehydrogenase (LDH), total cholesterol, triglycerides, ferritin, serum iron, total iron binding capacity (TIBC) and transferrin saturation (TSAT). Chemistries will be assessed monthly. eGFR will be determined on serum chemistry samples collected at the Screening, Baseline, Month 6, Month 9, and Month 12 (EOT) visits.

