## 3 STUDY DESIGNS

This is a Phase 2 randomized, double-masked, placebo controlled, multi-center study, to evaluate the safety and efficacy of 48 weeks of subcutaneous AKB-9778 administered 15 mg QD or 15 mg BID in subjects with moderate to severe NPDR. Exploratory evaluations include pharmacokinetic assessments, as well as exploratory efficacy assessments (OCT-Angiography (OCT-A), Ultra Wide-Field (UWF) imaging and non-invasive Electroretinography (ERG) at a subset of sites. Blood samples will be retained for biomarker and genetic analysis.

Subjects will participate in the study for approximately 56 weeks (screening period up to 4 weeks, baseline and treatment periods for 48 weeks, and follow-up period for 4 weeks). The study will be conducted at approximately 50 investigative sites. Subjects will be randomized 1:1:1 to either AKB-9778 15mg QD, AKB-9778 15mg BID, or placebo treatment groups. Fifty (50) subjects are planned per group. The treatment groups are as follows:

- Active Group: SC AKB-9778 15 mg (QD); To maintain masking, subjects will receive BID dosing with masked study medication administered as one dose of active and one dose of matching placebo.
- Active Group: SC AKB-9778 15 mg (BID)
- Placebo Group: SC phosphate-Buffered-Saline (PBS) (BID)

Subjects will self-administer study medication as subcutaneous (SC) injections in the abdomen (preferably) around the same time every morning and evening, if possible. The investigator, all study-site personnel, all Sponsor personnel (except for an unmasked CMC representative), Central Image Reading Center personnel, and subjects will be masked to treatment assignment during the entirety of the study. Randomization will be stratified by screening Early Treatment of Diabetic Retinopathy Study (ETDRS) Diabetic Retinopathy Severity Score (DRSS) (levels 4, 5 and 6 equally distributed among the treatment groups).

Spot UACR and eGFR will be assessed at baseline, and thereafter every 12 weeks as exploratory assessments to evaluate for any potential effects on renal function. Plasma samples will be collected at specified times on Day 1 and Month 6 visit for PK assessments. These samples will be analyzed for AKB-9778 using validated bioanalytical methods.

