## **10.2 Secondary, Exploratory and Exploratory Sub-Study Efficacy Endpoint Analysis**

Secondary efficacy endpoints are summarized in Section 5.2, and involve alternative analyses of DRSS results, showing the proportion of patients who develop sight-threatening complications of DR (DME & PDR). Measures of kidney function (UACR and eGFR) are exploratory efficacy endpoints. Exploratory sub-study endpoints are derived from OCT-Angiography, Ultra-wide field fluorescein angiography, Ultra-wide field color photographs, and electroretinography. Details of these variables and their analysis are contained in separate SAPs.

Normality assumption will be tested for any endpoint of continuous nature. If normality assumption is violated, appropriate transformation and/or non-parametric analysis will be employed. Otherwise, all secondary, exploratory and exploratory sub-study endpoints of continuous nature will be analyzed using ANCOVA model, and all inferential analyses will use a 2-sided 5% significance level. For the exploratory efficacy endpoints UACR and eGFR, for internal decision-making purposes, a 1-sided 10% significance level will be used. Whenever possible, a mixed model repeated measures (MMRM) model will be utilized to analyze this data. The model will include change from baseline as the dependent variable. The p-value and 95% CI from the model is baseline parameter adjusted.

For MMRM, visit will be treated as the repeated variable within a subject. Within-subject error, an unstructured variance-covariance will be applied; in case of non-convergence, compound symmetry will be used. MMRM model for UACR and eGFR is adjusted by the baseline HbA1c, Baseline Systolic BP, log-transformed Baseline UACR, and ACEi/ARB use.

Secondary, exploratory and exploratory sub-study endpoints of a dichotomous nature will be analyzed using the same approach as outlined for the primary efficacy endpoint.

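### eGFR is measured twice before dosing but the SAP uses only the last value, so the exploratory eGFR analysis gives up some precision; the SAP should also state that baseline eGFR is in the eGFR model

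*SAP*

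**What the plan says.** **Two pre-dose values.** Protocol 9.2.2 (chemistry item) states: "eGFR will be determined on serum chemistry samples collected at the Screening, Baseline, Month 6, Month 9, and Month 12 (EOT) visits". Protocol 6.1 and Appendix A, note L, give the same schedule. Protocol 9 places Screening at most 28 days before Baseline. SAP 3 restates the schedule without Screening: "Spot UACR and eGFR will be assessed at baseline, and thereafter every 12 weeks". (The SAP also implies a Week 12 eGFR that the Protocol does not schedule. That is a separate inconsistency.)

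**One is kept.** SAP 7.3: "In cases where more than one pre-dose observation has been recorded, the last recording will be identified as the baseline result". SAP Table 1 sets the baseline window for chemistry at Day 1 or earlier, so the Screening value falls inside it and is set aside whenever a Day 1 value exists. No rule averages the two.

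**Where the single value goes.** SAP 10.2 says of the model: "The model will include change from baseline as the dependent variable". SAP 5.3 also uses baseline eGFR to define the subgroup below 90 mL/min/1.73 m².

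**Covariates.** SAP 10.2 says in general terms: "The p-value and 95% CI from the model is baseline parameter adjusted". The next paragraph adds: "MMRM model for UACR and eGFR is adjusted by the baseline HbA1c, Baseline Systolic BP, log-transformed Baseline UACR, and ACEi/ARB use". Baseline eGFR is not named there. The SAP does not say whether this list adds to the general adjustment or replaces it.

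**The concern.** A single eGFR reading carries assay and day-to-day variation. That noise enters the change score, weakens the covariate and blurs assignment to the <90 subgroup. A second pre-dose reading is already scheduled for every subject, so a better baseline needs no new sample.

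The covariate wording raises a second question. If the named list is complete, the eGFR model adjusts for baseline UACR but not for baseline eGFR, and more precision is lost. Two programmers could build different models from the same paragraph.

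What is at stake is the precision of one exploratory comparison, which SAP 10.2 tests at a 1-sided 10% level for internal decisions.

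**Working it through.** **Plan's own figure.** The documents give no power, SD, correlation or target effect for eGFR. Their only power statement concerns the DRSS primary endpoint (45 per arm, 30% vs 5%, Fisher's exact test, above 85%). It reproduces at 86.3% and has no bearing on this point.

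**Set-up.** Work in units of the eGFR variance at one visit. Let r be the correlation of each pre-dose value with Week 48, and c the correlation between the two pre-dose values. Both are assumptions. Residual variance of the treatment comparison:

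- change score, no baseline eGFR covariate: 2(1 − r)
- ANCOVA on one baseline: 1 − r²
- ANCOVA on the mean of two baselines: 1 − 2r²/(1 + c)

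**Equal correlations (c = r).**

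| r | one baseline | both | fall in residual variance |
|---|---|---|---|
| 0.7 | 0.510 | 1 − 0.98/1.7 = 0.424 | 17.0% |
| 0.8 | 0.360 | 1 − 1.28/1.8 = 0.289 | 19.8% |
| 0.9 | 0.190 | 1 − 1.62/1.9 = 0.147 | 22.4% |

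**Pre-dose values closer to each other than to Week 48 (r = 0.80).**

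| c | one baseline | both | fall in residual variance |
|---|---|---|---|
| 0.90 | 0.360 | 1 − 1.28/1.90 = 0.326 | 9.4% |
| 0.95 | 0.360 | 1 − 1.28/1.95 = 0.344 | 4.6% |

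Across both tables the standard error falls by between 2% (1 − √0.954) and 12% (1 − √0.776).

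**Power.** Take an effect that has 80% power under one-baseline ANCOVA at 1-sided 10% with r = 0.8. With residual variance v, power is Φ(2.123·√(0.36/v) − 1.282).

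- both values, c = 0.80: v = 0.289, power 86.2%
- both values, c = 0.90: v = 0.326, power 82.9%
- both values, c = 0.95: v = 0.344, power 81.4%
- no baseline eGFR covariate: v = 2(0.2) = 0.40, power 76.8%

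**If baseline eGFR were really absent.** At r = 0.8, moving from the change score to one-baseline ANCOVA lowers variance by 1 − 0.36/0.40 = 10%. Moving to both values under equal correlations lowers it by 1 − 0.289/0.40 = 28%. These figures apply only under that reading of SAP 10.2.

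**Other covariates.** In a simulation with 45 per arm, 4,000 replicates and r = c = 0.8, entering both values cut variance by 19.6% when the other covariates were unrelated to eGFR. It cut variance by 16.8% when one of them correlated −0.4 with the underlying eGFR level.

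**A trap in the remedy.** Keeping change from the Day 1 value while adjusting only for the two-value mean gives 2(1 − r) − (1 − r)²/[2(1 + r)] under equal correlations. At r = 0.8 this is 0.40 − 0.04/3.6 = 0.389, which is 8% worse than the 0.36 of one-baseline ANCOVA. The simulation gave about 9% worse. The mean must therefore be used for both the change and the covariate, or both values must be entered.

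**The case against.** Taking the last pre-dose value is a standard, prespecified rule, applied alike to all variables and arms. It creates no bias between randomised groups. It also keeps UACR, which has no Screening sample, and eGFR on the same Day 1 baseline within a shared model specification. The endpoint is exploratory. The two pre-dose readings are at most 28 days apart while Week 48 is nearly a year later, so they may well correlate more with each other than with the outcome, and the gain may then be in single digits. All of this stands, and it makes the point an optional improvement rather than a correction.

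A reader might infer from the named covariate list that the eGFR model omits baseline eGFR. The documents do not establish that: "The p-value and 95% CI from the model is baseline parameter adjusted" appears in the same section and most naturally puts each outcome's own baseline in its model. On the other side, the list names log baseline UACR, which would be redundant for the UACR model if the general phrase already supplied it. The text is ambiguous, and one sentence would settle it.

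A reader might also take the 20% at r = 0.8 as the share of the achievable variance reduction that is lost. It is not. One baseline removes 0.640 of the variance and two remove 0.711, so the share forgone is 0.071/0.711, or 10%. The 20% is a fall in residual variance.

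**Conclusion.** The point holds as a small, nearly free gain in precision on an exploratory endpoint. Against an ANCOVA that already includes one baseline eGFR, using both values lowers residual variance by about 5–22%. The upper part (17–22%) needs equal correlations of 0.7–0.9 among all visits. The lower part (about 5–9%) applies if the pre-dose values correlate 0.90–0.95 with each other and 0.80 with Week 48. The documents do not say which case is closer. Assignment to the <90 subgroup would also rest on a less noisy value, but that gain has not been quantified.

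There is no bias, and no primary or secondary conclusion depends on this.

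A reader might extend the argument to IOP and BCVA, which are also read at Screening and on Day 1. The documents do not support that. Both are safety endpoints, SAP 11 specifies summaries of change and shift tables rather than a treatment contrast for them, and no gain has been shown.

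**What to change.** In SAP 7.3 and 10.2, for eGFR only:

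1. Define baseline eGFR as the mean of the Screening and Baseline values, or the single value if one is missing. Use it for the change score, the <90 subgroup and the covariate. Alternatively, enter both values as covariates and state which baseline defines the subgroup. Do not pair change from Day 1 with adjustment for the mean alone.
2. State that baseline eGFR is in the eGFR MMRM in addition to HbA1c, systolic BP, log-transformed UACR and ACEi/ARB use.

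The second item is worth doing even if the first is declined. Both should be settled before unmasking. After that, the two-value version belongs in a labelled sensitivity analysis.

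The cost is one extra derivation and a little SAP text, with no added data. The small downside is that the eGFR baseline would be defined differently from the UACR baseline.

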## **8 DISPOSITION AND EXIT STATUS**

### **8.1 Subject Disposition**

Subjects who are enrolled, complete the study, discontinue study medication, or withdraw from the study including reasons for study medication discontinuation or study withdrawal will be summarized along with the number and percentage of subjects in each of the analysis populations (safety, PP, PK and sub-study) in tabular format by treatment group and for all subjects. The number and percentage of subjects who completed 1-month follow-up visit will be summarized in the Safety population. The reasons for active treatment period discontinuation that will be summarized include: adverse events, treatment for PDR or DME, subject withdrew consent, lost to follow-up, protocol deviation, termination of study and other. Individual subject disposition data will be listed.

### **8.2 Extent of Study Drug Exposure**

Exposure to treatment and treatment compliance will be summarized by treatment group and for all subjects. A listing will present all product accountability details. Duration of exposure is determined from the dispensed and return date information. Treatment compliance is determined as the number of actual doses received over the number of expected doses multiplied by 100. Expected subcutaneous study medication doses is twice the date of the last date of dosing minus the date of the Day 1 visit plus 1 (minus allowed days of non-dosing, i.e., days on which subject was intentionally not dosing per Investigator instruction/allowance, due to safety/tolerability or concomitant illness/procedure/hospitalization). The number and percentage of subjects who are at least 70% compliant will be summarized.

### **8.3 Protocol Deviations**

The number and percentage of subjects with major protocol deviations will be summarized by treatment groups and for all subjects for the safety population. The protocol deviations that will be summarized include: informed consent, inclusion/exclusion and randomization, study drug administration and assignment at site, improper protocol procedures at site (missed, repeated, not per protocol), site's failure to report SAE/AE, visit out of window (missed, early, late), subject's non-compliance with subcutaneous study drug (<70% of expected doses administered), subject's use of prohibited concomitant medication, subject's failure to follow instructions and other. A subject listing will be provided that includes the date of the deviation, the deviation description and the classification of whether the deviation was judged to be major or minor.

### **8.4 Exclusion from Analysis Populations**

The number and percentage of subjects that are excluded from Per Protocol Population due to protocol deviations, did not complete study and non-compliant will be summarized for the MITT population by treatment groups and for all subjects. The number of subjects with percentage excluded from pharmacokinetic population because of non-evaluable data will also be presented for MITT population by

treatment groups and for all subjects. A listing for the subjects excluded from MITT population will be generated.

## **9 BASELINE CHARACTERISTICS**

### **9.1 Demographics and Baseline/Screening Characteristics**

All demographic and baseline data will be summarized per treatment group and overall. These will be presented for the safety population and MITT population separately. The demography presentation will include Age (years), Sex, Ethnicity, Race, and BMI (kg/m^2). Summary statistics of duration of diabetics (years), and the types of diabetics will be presented. The duration of NPDR (years), DRSS and BCVA will be summarized for the study eye. Number and percentage of subjects with right eye (OD) and left eye (OS), and prior treatment of PDR or DME in study eye will also be summarized. Additionally, the number and percentage of subjects who were taking insulin and ACEi/ARB will be presented by the treatment group and for all subjects.

### **9.2 Prior and Concomitant Medications**

Prior and concomitant medications will be presented for each subject coded per the World Health Organization (WHO) Anatomical Therapeutics Chemical (ATC) Drug dictionary. Prior medication are those medications that were started anytime and were stopped within 30 days prior to visit 1. Concomitant medications are those medications that were started anytime after visit 1 and before the last study visit or started anytime before visit 1 and were ongoing on or after visit 1. The data will be summarized by ATC dictionary (WHO DDE B2 September 1, 2017) drug class and generic name and classified as non-ocular and ocular prior and concomitant medications. Further, ocular prior and concomitant medications are presented for study eyes, qualified fellow eyes and unqualified fellow eyes. Descending sorting order by the frequency of ATC drug classification, and within that descending order by the frequency of generic name will be followed. A separate listing for both non-ocular and ocular prior and concomitant medication will present be presented.

Medications with partial dates that do not allow determination of whether prior or concomitant will be considered concomitant. Prior and concomitant medications are presented for safety population.

### **9.3 Medical History**

Medical history will be coded using the Medical Dictionary for Regulatory Activities (MedDRA) version 20.1 Non-ocular medical history will be summarized using discrete summary statistics and presented by treatment groups and for all subjects by System Organ Class (SOC) and Preferred Term (PT) using safety population. Ocular medical history will be similarly summarized by treatment groups and for all subjects for the study eyes, qualified fellow eyes, and unqualified fellow eyes separately. Subjects with multiple medical histories in the same SOC or PT will be counted only once for the respective SOC or PT. Subject listings of medical history will be generated separately for ocular and non-ocular data.

